## 2) Objectives

Autism Access Link for Early Referral and Treatment [ALERT], the intervention proposed in this application, is a novel state-wide referral and case management platform that PCPs can activate to ensure that a child with suspected Autism Spectrum Disorder (ASD) receives all necessary ASD diagnosis and treatment resources in a single referral, radically simplifying a complex diagnostic and treatment process. We hypothesize that Autism ALERT will have strong acceptability and high rates of use among primary care providers as well as among diverse low-income patients of children at risk for ASD, and that we will see higher rates of child ASD educational evaluations within six months, and shorter time between referral and ASD treatment,.

## 3) Background

Children with ASD can be accurately identified as early as two years old. Children identified early and placed promptly into comprehensive treatment models [CTMs] such as applied behavioral analysis programs, show improvements in language, IQ and adaptive functioning. Still, average age of ASD diagnosis in the US is around 4 years old, and is older for low-income and racial/ethnic minority children. Low-income and minority children are also less likely to be diagnosed with ASD, and are more likely to have severe features (e.g. comorbid intellectual disability). Although access to evidence-based ASD therapy is rapidly expanding, most children with ASD are not treated with evidence-based interventions, and minority children use Early Intervention and CTM therapies at the lowest rates. Thus, there is a strong need for interventions that connect low-income and minority children with existing services that they are eligible for and could access. Primary-care based screening for ASD and other developmental delays is increasing. As a result, more children with suspected ASD are identified and referred from primary care. However, unlike other conditions for which early identification and treatment are critical (e.g., hearing impairment, congenital metabolic disorders), there exist no statewide or national systems to ensure that children identified with ASD risk are promptly evaluated and treated. While ASD services are theoretically available for most children in the US, they are often not accessed, leaving a critical gap between identification of suspected ASD in primary care and access to ASD diagnostic and treatment services, particularly for low-income and minority children. Research by our team suggests that this gap exceeds 2 ½ years on average. However, our prior research has also shown that when PCPs help families connect with ASD services, ASD diagnosis and treatment is timelier, and timely diagnosis is associated with increased use of evidence-based services. As a result, we propose a model statewide intervention to close the gap between identification of suspected ASD in safety-net (i.e., underserved setting) primary care clinics and use of diagnostic and treatment resources, for low-income and minority children.

## 4) Study Design

We propose a pilot clustered interventional trial with two arms. Clinics in the intervention arm receive Autism ALERT plus an ASD screening intervention (START Autism), and clinics in the comparison intervention (control) arm receive only START Autism (no Autism ALERT). As this is a pilot trial, primary outcomes of interest are feasibility and acceptability. We will additionally assess mechanism of outcome, preliminary efficacy, and protocol fidelity. Feasibility and acceptability will be assessed in intervention clinics. Mechanism of action and preliminary efficacy will be assessed by comparing intervention to control clinics. Fidelity is assessed in both arms. We will pilot test Autism ALERT in 6 safety-net primary care clinics in Oregon: 3 clinics will serve as intervention clinics, receiving both Autism ALERT and START Autism, and 3 clinics will serve as controls receiving START Autism only. Study arm will be assigned via coin-flip randomization of clinics, stratified for size and urbanicity, by a statistician who is not otherwise part of the study team.

In 2023 we received new funding from CareOregon to expand the project. As a result, this pilot study will be expanded to all of Portland-metro area. It will no longer include a control arm. Participants will be recruited off of Autism clinic waiting lists in the PDX metro area, and will be enrolled into the study to receive family navigation services from our partners at Help Me Grow.

## 5) Study Population

### a) Number of Subjects

The three subject groups include clinics, child/parent dyads, and providers. We seek to enroll 7 safety net primary care practices. 70 child/parent dyads will participate in this study (20–baseline condition, 25–intervention, 25–control). We estimate that 30 providers will participate in this study (15–intervention; 15–control). The number of participants per site will depend on the size of the participating clinics.

Per the expansion to all of Portland-metro area, we estimate that there will be around 300 children enrolled in the next 3 years.

### b) Inclusion and Exclusion Criteria

There are different eligibility requirements for clinics, children/parents, and providers.

To meet eligibility criteria, participating clinics must have >30% Medicaid enrollees or uninsured patients. Family medicine clinics must have >30% children. The study will be initially offered to safety-net primary care practices in 3 Oregon counties. We seek to enroll 6 clinics; if more than 6 clinics initially express interest, we will randomly choose 6 interested clinics, reserving at least two spots for non-metropolitan clinics. If fewer than 6 express interest, we will open recruitment to an additional two counties. Additional counties will be considered if recruitment is inadequate.

Child/parent dyads are eligible for inclusion when the child's PCP suspects the child has ASD. This can be for any reason, including the child having a high-risk ASD screen, or clinical concern. Children with prior ASD diagnoses or prior history of diagnostic evaluation for ASD are excluded. Enrolled children must be between age 12 and 54 months at enrollment to ensure EI/ECSE eligibility.

Provider subjects must be pediatric primary care providers (e.g., physician, nurse practitioner, physician assistant) licensed in Oregon, and must see children age 1-5 for well-child care. Subspecialists are excluded.

For the expansion, any child aged 1-5 years old on an Autism clinic waiting list at OHSU, Randall Children's Hospital, Providence Child Development Institute, Mindsights, or The Children's Program, or a referral from an Autism ALERT trained provider is eligible to join the study, if they have not previously been medically diagnosed with Autism.

### **c) Vulnerable Populations**

This study will include children under 7, as described in the inclusion criteria. The study may also incidentally include pregnant women, as there are no exclusion criteria for the parent in a child/parent dyad. However, pregnancy is not a focus of the study. We will not obtain information about parent pregnancy status as part of this research. The study excludes neonates, decisionally impaired adults, and prisoners.

### **d) Setting**

Autism ALERT services will be administered through Help Me Grow (HMG) Oregon. HMG is a national model system promoting optimal early childhood development via cross-system connectivity. Universal HMG components include: a centralized telephone access point to help families and professionals connect children with community-based programs and services; family and community outreach to advance developmental promotion and grow awareness of developmental resources; healthcare provider outreach to support early detection and intervention; and data collection to support program evaluation, bolster advocacy, and guide quality improvement.

In Oregon, HMG is part of the Swindells Resource Center at Providence Portland Medical Center. Swindells is a statewide disability support organization with offices in Portland, the Columbia River Valley, and Southern Oregon. In addition to HMG, Swindells has a family navigation program for children with developmental disabilities with experienced family navigator staff. Swindells is located in the same building as Oregon Pediatric Society, which will oversee the comparison intervention. Thus, colocation of Autism ALERT and HMG within Swindells places Autism ALERT and its staff in a supportive environment that is rich in information about childhood disability, and which is poised for statewide dissemination. The study Navigators are employed by HMG and the Swindells Resource Center. Swindells staff involved in the project are considered part of the study team and have submitted (or will submit in the future, in the case of the navigators as they have not yet been hired) required training documents. An IAA is being requested with Providence.

Additional data will be collected through a chart review performed by administrators at participating clinics. The clinic administrators will be considered engaged in research, and will complete an Individual Investigator Agreement (IIA), in addition to completing an IRB and study procedures training from the study team. The administrator will be compensated at a rate of \$40 per hour at 6 sites and at a flat rate of \$200 at one site that would not allow hourly payment.

This study is being designed with input from [name], an advisor and collaborating researcher from Boston Medical Center. [name] will interact with the study team and may provide training to the Navigators, who are part of the study team, but she will not interact with

or interview subjects, she will not be involved in the consent process, and she will never have access to identifiable private research data.

The CareOregon funding will provide a means of expansion to help families navigate Autism diagnosis services in all of Portland-metro area. While navigation services will still be provided through Help Me Grow, the service areas will now include all of Portland-metro. Specifically, any child on an autism clinic waitlist, or any child who has received an autism clinic referral can access navigation services through our program.

### **e) Recruitment Methods**

The study has a clinic-based recruitment strategy. In order to assure that the intervention addresses the needs of diverse children who are underserved in autism care, study inclusion criteria mandate that participating clinics have at least 50% Medicaid or uninsured patients. In addition, to make sure sample size is adequate, Family Medicine clinics must have at least 30% children. Since one of the study's goals is to ultimately reduce racial and ethnic disparities in the early identification of ASD, we will strive to attain a racially and ethnically diverse family sample by specifically approaching clinics that serve a diverse patient base, including recruiting clinics in rural areas. Autism ALERT will initially be offered to all Oregon primary care clinics meeting inclusion criteria in selected counties. We seek to enroll 6 clinics; if more than 6 clinics initially express interest, we will randomly choose 6 interested clinics, reserving at least two spots for non-urban clinics. If fewer than 6 express interest, we will open recruitment to additional counties. In this way, we hope to recruit a sample that would be representative of primary care clinics who will ultimately participate in a larger-scale study.

Clinics will be recruited to the study with the help of the Oregon Pediatric Society. They will be approached initially via an approved recruitment email (see "Autism ALERT Email Templates"). The recruitment process will include a training session for all clinic staff, at which initial provider surveys and patient study packets will be distributed.

Families will initially receive a study packet from their provider at the time of the referral. The packet will contain a children's book, information about autism, an Early Intervention Referral Form, and a Study Interest Form. Aside from the study interest form and the phone scripts that are used for screening there are no other recruitment materials (e.g., emails, flyers) for family participants at this time. They will learn about the study first from the study interest form. The Study Interest Form will include some general information about the study, as well as a HIPAA authorization allowing disclosure of family contact information and some health information to the study team. The parent will sign the interest form, allowing the clinic to pass the family's contact information to the Navigator team. Navigators will then reach out to the family to complete the online consent process, or phone consent process as necessary (see more information below). Please see Family Consent Form attachments. Family enrollment will be incentivized with a children's book and \$50 stipend per survey completed for both experimental and control groups. Provider participants may receive Continuing Medical Education credits and/or Part IV Maintenance of Certification credits, if desired, as part of their participation in this study. Clinics may also be entered into a raffle to incentivize their patients' referral to the study, based on whether they refer any patients to the study in a given time period. The raffle incentive will be a gift or food basket costing less than \$100. Control arm clinics will also be given a box of chocolate on Valentine's day to further increase enrollment as enrollment is lagging in that arm.

For clinics in the OHSU system, referrals to the Autism diagnostic clinic will also be monitored for potential study recruitment. The diagnostic clinic staff will provide a list of MRNs of patients referred to the OHSU Autism Clinic, which will be transmitted via secure OHSU emails to the referring primary care provider and study team for inclusion in the study. Data will be transmitted as a list of MRNs, which the provider can use EPIC to identify and consider. If the provider gives permission, the study team will directly contact the family. No PHI will leave OHSU.

For the expansion, we will be recruiting participants through Autism clinic waitlists. We already have access to Providence and OHSU system waitlists as study staff are at both sites. We are requesting a HIPAA waiver to access patient contact information for all sites. We will contact participants off the waitlist to enroll in the study. We will also be providing Autism screening training to providers and clinics in Portland-metro who express interest. These providers will also be receiving CME credits. These providers can then refer children they suspect may have Autism to our project, in addition to sending in a referral to their nearest Autism clinic.

We will be contacting autism clinics to see if they would like to offer Autism ALERT enrollment to families from their site; if so a HIPAA Waiver will be completed for that site. If a family is intended to be recruited off the autism clinic waitlist, we will also be sending them an advance letter through either email or mail 2 weeks before proceeding to call them for enrollment. If possible, we will also attempt to contact parents through their Electronic Health Record portal such as MyChart. They will be instructed to contact the study team if they would like to opt-out via email, text, or phone.

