##### Families:

The consent process for families (in the intervention and control groups) was different than that for primary care providers. Families for whom ASD is suspected will be handed a study interest form by their PCP. The PCP will ask if they are interested in learning more about the study. If so, they will indicate their interest by completing a study interest form. This study interest form will serve as authorization to allow the PCP to release information to the researchers for recruitment purposes. This signed interest form signifies study interest but is not a consent for the study. Interested parents will then be contacted by the study team via phone, text or email, to secure electronic signed consent or verbal consent.

Text messaging, using the secure Twilio app hosted by OHSU, will be utilized for scheduling phone calls. Text messaging will not be used to obtain consent but will be used to schedule a phone appointment to obtain consent. After consenting, the family may also choose to receive text messages from the navigator or study team with updates, reminders, or other scheduling requests.

**Electronic consent:** Families will sign consent electronically through a form built in Research Electronic Data Capture (REDCap). The software allows consent forms to be emailed directly to the email address that the participant provides upon signing the Study Interest Form. Per OHSU OCTRI requirements, participants will click a radio-box for yes or no, and if yes is selected, will enter their first and last name. This will be used in conjunction with the timestamp on the REDCap form to confirm consent to the study. In most cases, participants will provide electronic consent while on the phone with a Navigator, who will be able to confirm their identity through phone, email, and signature congruency.

**Verbal Consent over the Phone:** For families lacking internet access, a verbal consent via telephone will be provided in lieu of electronic signed consent. For these families we have requested a HIPAA waiver/alteration.

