The research team will repeatedly emphasize to community providers and study team members that participation is optional, and that families should not be coerced to participate. Given that many families of children at risk for autism have low literacy and/or limited English proficiency, all study materials including consent documents will be available at a 6th grade reading level in English and Spanish, and a study research assistant and family navigator will speak both languages fluently. Families speaking languages other than Spanish or English cannot enroll in the study but can be referred to Swindell's existing family navigation services (not part of the research study) if PCPs choose. We cannot enroll non-English/non-Spanish speakers in the study, because from a scientific standpoint their resource use would be quite different. In addition, the low numbers of enrollees in this group might create imbalances in the intervention and control arms that would make data interpretation challenging.

Pregnant women are only enrolled incidentally as part of the general parent study population; no study procedures will entail any risk to pregnant women or their fetuses. This project will not enroll human fetuses, neonates, or prisoners.

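### In the controlled pilot, one consent process for both arms routinely puts control families in contact with the navigators who deliver Autism ALERT, and nothing limits or separately counts that contact

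*Protocol*

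**What the plan says.** Protocol section 4 (Study Design) sets three intervention clinics against three control clinics and states that "clinics in the comparison intervention (control) arm receive only START Autism (no Autism ALERT"). Section 5 d) (Setting) says that "Autism ALERT services will be administered through Help Me Grow (HMG) Oregon" and that "The study Navigators are employed by HMG and the Swindells Resource Center".

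Section 5 e) (Recruitment Methods) sends the contact details on the signed interest form to the navigator team, after which "Navigators will then reach out to the family to complete the online consent process". The same paragraph goes on to family incentives for both arms and gives control families no other route.

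Section 5 f) (Consent Process, Families) opens by naming both arms: "The consent process for families (in the intervention and control groups) was different than that for primary care providers". It says "Interested parents will then be contacted by the study team via phone, text or email", and then, of electronic consent, "In most cases, participants will provide electronic consent while on the phone with a Navigator". On language it says that "a study research assistant and family navigator will speak both languages fluently".

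**The concern.** Access to a family navigator is a main part of what separates the arms at family level. If the same navigators telephone control families to take consent, the control condition includes a conversation with intervention staff that the design did not intend. A parent worried about autism may well ask questions on such a call, and a navigator whose job is to connect families with services may well answer them.

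At stake are the comparisons between arms: family experience, changes in stress and empowerment, preliminary efficacy including time to treatment, and the standardised effect size that section 8 (Data Analysis) intends for planning the R01. Help given to controls would pull these differences towards zero.

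**Working it through.** The protocol states no contamination rate, target effect or power calculation, so there is no figure to reproduce. The check is a comparison of sections.

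1. **Which arms the process covers.** Section 5 f) describes two consent processes, one for providers and one for families, and assigns the family process to both arms.
2. **Who makes contact.** Section 5 e) names navigators without restriction by arm. Section 5 f) says the study team makes contact and then makes a navigator on the telephone the usual case. The two wordings are compatible, because section 5 d) counts the Swindells staff on the project as study team and section 6 (Procedures) says the same of the navigators. The usual-case statement is not split by arm, so the share of control families consented by a navigator is unknown.
3. **What controls should receive.** Section 4 gives them START Autism alone. Section 8 examines experience with navigators only in the intervention arm, and section 10 b) (Potential Benefits) attributes expected gains in empowerment and self-efficacy to having a navigator. The plan therefore treats navigator contact as belonging to one arm.
4. **Whether the contact is limited.** Section 5 e) mentions telephone scripts for screening, whose content is not in the protocol. No section restricts a navigator to consent matters on a control call. Section 5 f) also lets families, after consent, receive texts from the navigator or the study team, again without distinguishing arms.
5. **Whether it is counted.** Sections 6 and 8 have navigators record their interactions with families, with counts of contact attempts and activities and a cross-check against recorded calls. Section 4 assesses fidelity in both arms. None of this calls for a separate tally of navigator contact with controls.
6. **Which results depend on it.** Section 4 assesses feasibility and acceptability in intervention clinics, and mechanism and preliminary efficacy between arms. Only the between-arm results are exposed.
7. **Direction and size.** Let D be the true difference, c the share of controls who receive help, and k the fraction of the full ALERT benefit that this help gives. The expected observed difference is D × (1 − c × k). For c and k above zero it is smaller than D, which fixes the direction. The protocol gives none of the three quantities, so the size cannot be calculated.

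**The case against.** The strongest reply is that contact is not treatment. No section says that a navigator helps a control family, and section 4 says that control clinics receive no ALERT. That stands. A reader might infer that control families were navigated, or were left with a navigator to call back; the protocol supports neither. What it documents is contact with intervention staff, which makes contamination a risk and not a fact.

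Second, navigators need not be the only callers. Section 5 f) refers to the study team, the route for OHSU clinics in section 5 e) has the study team contact families directly, and a research assistant is mentioned. This also stands in part: some controls may have been consented by others. It does not displace the statement that a navigator is on the telephone in most cases.

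Third, the comparison is imprecise anyway. With the planned 25 dyads per arm, and assuming proportions near 50%, the standard error of a difference is √(0.25/25 + 0.25/25) = 0.141. The 95% interval is then about ±1.96 × 0.141 = ±28 percentage points before any allowance for clinic clustering. Section 8 says openly that the pilot is not powered for significance. Modest dilution would be hard to see against that. This lowers the priority, but it does not excuse an avoidable bias of known direction in an estimate meant for planning.

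Fourth, changing the caller does not blind anyone. Arm is set by clinic, so a research assistant who knows the referring clinic would normally know the arm. Primary care providers choose which families to offer the study before any call. Families first hear of the study from the interest form, and Help Me Grow and Swindells offer help outside the trial. All of this is correct, so the fix should not be presented as a remedy for selection or for awareness of the service.

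**Conclusion.** The point holds as a limited design weakness of the controlled pilot. As written, the consent process routinely puts control families in contact with the staff who deliver ALERT, and the protocol neither bounds nor separately counts that contact. Any help given would tend to understate the between-arm differences and the Cohen's d derived from them. The size is unknown, and a percentage dilution or an inflation factor for the R01 sample size would rest wholly on invented inputs.

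This rests on reading the both-arms wording of section 5 f) as applying to the navigator calls described in the same section, which is its natural sense. The primary outcomes are little affected, and the expansion is outside the point because it has no control arm. Section 5 e) also reports lagging control-arm enrolment. A reader might infer that navigator-led consent caused it, but nothing in the document links the two.

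**What to change.** For any consent still to be taken in the controlled pilot, have the bilingual research assistant foreseen in section 5 f) make the consent call in both arms from one script. Bring a navigator in for intervention families only after consent. This reads the research assistant and the navigator as two different people; the wording should be made explicit. Sections 5 e) and 5 f) should then name the same caller.

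Where navigators have already consented control families, use the existing process and fidelity records to count those contacts and any help given. Report the count beside the between-arm effect sizes, so that whoever plans the R01 can judge how far the estimate may be diluted.

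The cost is one extra hand-off for intervention families, some research assistant time, a script edit and a tabulation from records that the protocol already plans to keep. If control-arm recruitment has closed, only the count and its reporting remain.
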